### **Analysis Method**

Data analysis using SPSS 20.0 software program with appropriate statistical test. Data taken during the study will be displayed according to the variable type. Numerical variables with normal distribution will be displayed as mean  $\pm$  standard deviation, which is then analyzed by a general linear model (GLM) test for data measured more than once (IL-6, Beclin-1, Caspase-3, a- vO2 diff, and ScvO2) and independent t test for data with one time measurement (mortality rate in hospital and effective lactate clearance). Numerical variables with abnormal distribution will be shown in median (minimum-maximum) and then analyzed by Mann-Whitney test. The categorical variable will be displayed as a percentage (number) and will be analyzed by chi-square test or alternate test.

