### **Withdrawal or Discontinuation Criteria**

1. Patient dies prior to intra aortic balloon pump insertion
2. Treatment termination requested by family
3. Anemia due to hemorrhage with a decrease in Hb > 3 g / dL
4. Ankle brachial index (ABI) less than 0.8

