### **Procedures**

1. Patients who meet the criteria and agree to participate in the study taken as the subject of the research.
2. Research subjects were then randomized into two groups. The control group (Group A) and the treatment group (Group B) as the group that receiving intra aortic balloon pump (IABP) as early as possible within 3 hours after the return of spontaneous circulation (ROSC). IABP insertion is performed by an interventionist.
3. Baseline data such as age, weight, height, risk factor (hypertension, Diabetes Mellitus,

dyslipidemia, smoking, family history), history of Acute Myocardial Infarct (AMI), Percutaneous Coronary Intervention (PCI), Coronary Artery Bypass Graft (CABG), and valvular disease will be taken. Vital signs examination and EKG 12 leads will be performed.

- Laboratory tests for peripheral venous blood include: Lactate levels, urea (Ur), creatinine (Cr), n-terminal pro B-type natriuretic peptide (NT Pro BNP), high sensitive troponin (Hs Trop), IL-6, beclin 1 and caspase 3.
  - Central venous blood examination for central venous blood gas analysis includes assessment of a-vO2 diff and ScvO2.
  - Arterial blood examination for arterial blood gas analysis.  
Monitoring of hemodynamic parameters using echocardiography machines (ejection fraction, TAPSE, cardiac output, VTI).
4. In the group B, IABP is initiated within 3 hours after the return of spontaneous circulation by the interventionist.
  5. Blood sampling is repeated at 6th hour post ROSC or 1 hour post-insertion of IABP consisting of:
    - Laboratory tests for peripheral venous blood include lactate, IL-6, beclin-1 and caspase 3 levels.
    - Central venous blood examination for central venous blood gas analysis includes assessment of a-vO2 diff and ScvO2.
    - Arterial blood examination for arterial blood gas analysis.  
Examination of hemodynamic parameters with echocardiographic machine was repeated at the 6th hour post ROSC, consisting of ejection fraction, TAPSE, cardiac output, VTI).
  6. Research subjects will be monitored during hospitalization.

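### The analysis of markers measured at baseline and once more is left open and is not stated to use the baseline; a pre-specified ANCOVA on a suitable scale is at least as precise, at no extra sampling

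*Combined protocol and SAP*

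**What the plan says.** Procedures, item 3, takes a baseline panel that includes "high sensitive troponin (Hs Trop), IL-6, beclin 1 and caspase 3", together with a-vO2 difference and ScvO2 from central venous blood and four echocardiographic measures (ejection fraction, TAPSE, cardiac output, VTI). Item 5 repeats IL-6, beclin-1, caspase-3, lactate, the blood gases and the echocardiogram once.

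Analysis Method is the only analysis text. For normally distributed variables it plans a "general linear model (GLM) test for data measured more than once (IL-6, Beclin-1, Caspase-3" (the list goes on to a-vO2 difference and ScvO2), in contrast to an "independent t test for data with one time measurement (mortality rate in hospital and effective lactate clearance"). For the rest: "Numerical variables with abnormal distribution will be shown in median (minimum-maximum) and then analyzed by Mann-Whitney test". It gives no model terms, no covariate, and no statement of whether Mann-Whitney compares follow-up values or changes.

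On timing, item 5 states: "Blood sampling is repeated at 6th hour post ROSC or 1 hour post-insertion of IABP". Item 4 states that in Group B "IABP is initiated within 3 hours after the return of spontaneous circulation by the interventionist". For the echocardiogram there is only one clock: "Examination of hemodynamic parameters with echocardiographic machine was repeated at the 6th hour post ROSC".

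**The concern.** With one baseline and one follow-up value, the GLM as described could be any of three analyses:

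- an ANCOVA of follow-up on baseline;
- a repeated-measures model read from the group-by-time term, which with two occasions is a t test on change;
- the same model read from the group main effect, which is a t test on the average of baseline and follow-up.

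The Mann-Whitney branch has two readings, follow-up or change. Neither branch is stated to adjust for a baseline that is collected anyway. These tests differ in power, and with the term unstated the choice could be made after the results are seen.

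At stake is the precision of the markers that carry the circulation and tissue-perfusion part of the Aim. In-hospital mortality, the only designated outcome, is not touched.

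A separate matter is the two blood-sampling clocks. If they were applied differently by group, elapsed time would be mixed with the effect of the pump.

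**Working it through.** **Inputs.** From the documents: two randomised groups, one baseline value, one repeat. The documents give no sample size, SD, effect size or correlation, so there is no planned figure to reproduce. Everything numerical below rests on assumed values.

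**Step 1: variances.** Take equal SDs and correlation r, in units of 2·SD²/n with n per arm.

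- Follow-up only: 1
- Change (same as group-by-time): 2(1−r)
- ANCOVA: 1−r²
- ANCOVA relative to change: (1−r²)/[2(1−r)] = (1+r)/2
- Group main effect: the expected effect is halved and the variance is (1+r)/2, so its efficiency relative to ANCOVA is [0.25/((1+r)/2)]·(1−r²) = (1−r)/2

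| r | ANCOVA / follow-up | ANCOVA / change | Main-effect efficiency |
|---|---|---|---|
| 0 | 1.00 | 0.50 | 0.50 |
| 0.2 | 0.96 | 0.60 | 0.40 |
| 0.3 | 0.91 | 0.65 | 0.35 |
| 0.5 | 0.75 | 0.75 | 0.25 |
| 0.7 | 0.51 | 0.85 | 0.15 |
| 0.9 | 0.19 | 0.95 | 0.05 |

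**Step 2: patients per arm for 80% power.** Assume an effect of 0.6 SD, two-sided 5% and 1:1 allocation. Then n = 2(1.96+0.84)²·factor/0.6², about 43.6 × factor. The main effect uses 0.3 SD and factor (1+r)/2.

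| Test | r = 0.3 | r = 0.5 | r = 0.7 |
|---|---|---|---|
| Follow-up only | 44 | 44 | 44 |
| Change / group-by-time | 62 | 44 | 27 |
| ANCOVA | 40 | 33 | 23 |
| Group main effect | 114 | 131 | 149 |

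**Step 3: dependence on n.** Simulated power on the normal scale, effect 0.6 SD, r = 0.3 / 0.5 / 0.7:

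| Test | 15 per arm | 30 per arm |
|---|---|---|
| Follow-up t test | 35 / 35 / 35% | 63 / 62 / 62% |
| Group-by-time | 26 / 35 / 54% | 49 / 63 / 85% |
| ANCOVA | 37 / 43 / 60% | 66 / 73 / 89% |
| Group main effect | 17 / 16 / 13% | 30 / 25 / 24% |

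At r = 0 ANCOVA gains nothing over follow-up: 35% against 36% at 15 per arm, and 61% against 62% at 30.

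**Step 4: skewed marker.** Simulated power with lognormal values, log SD 1.0, log shift 0.605, 45 per arm:

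| Test | r = 0.3 | r = 0.5 | r = 0.7 |
|---|---|---|---|
| Mann-Whitney, follow-up | 79% | 79% | 79% |
| Mann-Whitney, raw change (marker lowered) | 49% | 62% | 81% |
| Mann-Whitney, raw change (marker raised) | 66% | 79% | 94% |
| ANCOVA, log scale | 84% | 90% | 98% |
| Rank ANCOVA | 82% | 88% | 96% |
| ANCOVA, raw scale | 64% | 69% | 81% |

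At 15 per arm and r = 0.3, log ANCOVA has 38%. Mann-Whitney on follow-up has 33% with a continuity correction and 35% without it. With zero shift, rejection rates were 4.3 to 5.3% for the Mann-Whitney tests, the t test on log change and all three ANCOVA versions, so the differences are in power and not in validity.

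**Step 5: clocks.** Insertion is at most 3 hours after ROSC, so one hour after insertion is at most 3 + 1 = 4 hours after ROSC. The other clock is 6 hours. The gap is at least 6 − 4 = 2 hours. A planned insertion exists only in Group B, and neither clock is assigned to a group.

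**The case against.** Several objections have force.

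- **ANCOVA is not always better.** A reader might infer that it beats every reading of the plan. It does not: there is no gain over follow-up at r near 0, little over change at high r (5% of variance at r = 0.9), and raw-scale ANCOVA on a skewed marker falls below Mann-Whitney on follow-up at r = 0.3 and 0.5. This stands, and it is why the scale has to be fixed.
- **The GLM may already be an ANCOVA.** A reader might infer that the plan rejects baseline adjustment. The text does not say so; it leaves the model unstated. Only the Mann-Whitney branch cannot use the baseline.
- **Much of the spread comes from the group main effect.** Because the plan contrasts repeated with single measurements, group-by-time is at least as natural a reading. Without the main effect, the normal-scale gaps to ANCOVA at 45 per arm (log scale, shift 0.605) are 84−67 = 17, 90−81 = 9 and 98−96 = 2 points. This stands.
- **The echocardiographic measures may be covered.** They are measured twice but not listed; the parenthesis can be read as examples. Naming them removes the doubt.
- **The clocks are a different problem.** Agreed. A reader might infer that the groups are sampled at different times. The documents do not say that; they only fail to exclude it.
- **Consequence is limited.** The markers are not designated outcomes, the planned tests are not biased by lacking adjustment, and naming ANCOVA does not address multiplicity across measures.

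**Conclusion.** The point holds as one to consider. The tested term, the Mann-Whitney quantity and the use of baseline are all unstated, and a more suitable analysis is available from data already collected. On a suitable scale, ANCOVA is at least as precise as follow-up only or change (0.91 / 0.75 / 0.51 and 0.65 / 0.75 / 0.85 of their variance at r = 0.3 / 0.5 / 0.7) and far more precise than the group main effect. Against Mann-Whitney on follow-up at r = 0.3, the gain is only about 5 points of power (up to 5 at 15 per arm, 5 at 45). These sizes rest on equal SDs and on assumed n, effect and r, none of which the documents supply.

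Nothing here bears on in-hospital mortality, and nothing shows the planned marker tests to be invalid for want of baseline adjustment. Two limits remain under any of these tests. A difference in sampling time between groups would not be corrected. Patients who die before the repeat draw have no follow-up value (the withdrawal criteria include "Patient dies prior to intra aortic balloon pump insertion"), so the comparison is among those alive and sampled.

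**What to change.** In Analysis Method, replace the GLM and Mann-Whitney wording for repeated markers with:

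> For each marker measured at baseline and follow-up, including the echocardiographic measures, the follow-up value will be compared between randomised groups by ANCOVA with group as factor and baseline as covariate, with an adjusted difference and 95% CI. IL-6, beclin-1 and caspase-3 will be log-transformed and reported as geometric mean ratios; other measures will be analysed on their original scale, with rank ANCOVA replacing Mann-Whitney if residuals are clearly non-normal. Patients without a follow-up value, and the reason including death, will be reported by group.

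The check on residuals should be described in advance and made without reference to the group result. Effective lactate clearance may stay as planned, because it is already a derived single value. Reporting missing values does not solve the survivor-only comparison, and the results should say so.

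Separately, in Procedures, item 5, reconcile the two follow-up clocks so that both groups are compared at the same time since ROSC, and state how the baseline draw is timed in each group. Which time is intended is for the sponsor to settle.

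**Cost.** The analysis change is wording only: no added samples or patients, and ANCOVA is itself a general linear model. Reconciling the clocks also needs no extra samples, but it may alter sampling times, which is more than wording if sampling has begun.

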### **Anticipated Outcome**

Early insertion of intra aortic balloon pump will be improving in-hospital mortality rate of cardiac arrest patients with acute coronary syndrome.

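### The biomarker comparisons use only patients alive at the second blood sample, and the protocol leaves open whether that sample falls at the same time since ROSC in both arms

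*Combined protocol and SAP*

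**What the plan says.** All quotes are from the combined protocol and SAP.

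- **Analysis Method.** IL-6, Beclin-1, Caspase-3, a-vO2 difference and ScvO2, if normally distributed, go to a "general linear model (GLM) test for data measured more than once". Non-normal variables go to Mann-Whitney. Effective lactate clearance is listed for a t test. The section gives no rule for a missing second value, none for death before it, and no analysis set. The form of the GLM and the contrast of interest are not stated.
- **Procedures, item 5.** "Blood sampling is repeated at 6th hour post ROSC or 1 hour post-insertion of IABP". Neither time is assigned to an arm.
- **Procedures, item 4.** "In the group B, IABP is initiated within 3 hours after the return of spontaneous circulation". An insertion is described for Group B only.
- **Procedures, echocardiography.** "Examination of hemodynamic parameters with echocardiographic machine was repeated at the 6th hour post ROSC", with no post-insertion alternative.
- **Withdrawal or Discontinuation Criteria.** The list includes "Patient dies prior to intra aortic balloon pump insertion", which by its wording can apply only to patients assigned IABP. Whether withdrawn patients stay in the analysis is not stated.
- **Anticipated Outcome.** "Early insertion of intra aortic balloon pump will be improving in-hospital mortality rate".

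**The concern.** A standard two-time-point repeated-measures GLM uses only patients with both values. Mann-Whitney on the second value or on the change needs the second value too, and so does lactate clearance. The comparison is therefore made among patients who survived to the second sample. Survival is a post-randomisation event that the trial expects the treatment to change, so randomisation no longer guarantees comparable groups.

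The open choice of sampling time adds two problems if the arms are in fact sampled at different times. A Group A patient who dies at hour 5 is lost while a Group B patient who dies at hour 5 is kept. The markers are also compared at different times since ROSC even if nobody dies.

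The Aim is improved prognosis by way of circulation and tissue perfusion, so these markers carry the trial's mechanistic claim.

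**Working it through.** The plan states no sample size, SD, early death rate or effect size, so there is no figure to reproduce. **Every rate, correlation and arm size below is an assumption.**

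**1. Timeline (from Procedures).** Group B: insertion by 3 h, plus 1 h, gives a sample at 4 h or earlier. Group A: no insertion, so 6 h. The possible gap is at least 6 − 4 = 2 h.

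**2. Bias in change with no treatment effect.** Let a latent frailty, standard normal, remove the frailest share d of an arm before the second sample. Let the marker change have correlation ρ with frailty. The mean change among survivors is −ρ·f(d) SD, where f(d) = φ(z₁₋d)/(1 − d). The bias, B minus A, is ρ·[f(d_A) − f(d_B)].

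- f(0.10) = 0.1755/0.90 = 0.195
- f(0.20) = 0.2800/0.80 = 0.350
- f(0.30) = 0.3477/0.70 = 0.497
- With the same hazard in both arms and 30% dead by hour 6, deaths by hour 4 are 1 − 0.70^(4/6) = 0.212, and f(0.212) = 0.2895/0.788 = 0.367

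| Setting | f(d_A) − f(d_B) | Bias at ρ = 0.2 | ρ = 0.4 | ρ = 0.6 |
|---|---|---|---|---|
| Same hazard, 30% dead by 6 h, both arms sampled at 6 h | 0 | 0 | 0 | 0 |
| Same hazard, 30% dead by 6 h, A at 6 h, B at 4 h | 0.130 | 0.03 | 0.05 | 0.08 |
| Deaths before second sample 20% (A) v 10% (B) | 0.155 | 0.03 | 0.06 | 0.09 |
| Deaths before second sample 30% (A) v 10% (B) | 0.302 | 0.06 | 0.12 | 0.18 |

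In this model the bias makes the arm that loses fewer patients look worse. Simulated type I error of a t test on change, which equals the group-by-time term with two times (nominal 5%), at 30, 60 and 100 per arm:

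- 20% v 10%, ρ = 0.4: 6.4%, 6.2% and 6.8%
- 30% v 10%, ρ = 0.6: 10%, 16% and 22%

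**3. When the bias is absent, and when it appears without unequal deaths.**

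- ρ = 0 with unequal deaths: bias 0.
- Death depends only on the baseline level and change is independent of it (20% v 10%): the group-by-time contrast has bias 0.000, but the group main effect is shifted by 0.15 baseline SD. The unstated contrast therefore matters.
- Equal deaths of 10%, with ρ = 0.6 in A and 0 in B: bias 0.6 × 0.195 = 0.12 SD.

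**4. What the baseline sample does.** Assume severity loads 0.7 on the second value and 0.8 on early death (product 0.56), with 50 per arm and a true benefit of −0.40 SD.

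- Second sample compared alone: −0.319 (20% v 10% deaths) and −0.279 (30% v 15%).
- Change from a baseline with the same loading of 0.7: −0.402 and −0.401. With no effect, type I error is 4.6% and 5.6%.
- Change from a baseline with a loading of 0.3: bias of about 0.04 to 0.08 SD.

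**5. Behaviour of a worst-rank Mann-Whitney test (death before the second sample ranked worst).**

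- Arm-specific times, equal hazards, no effect on anything, 30% dead by 6 h, B sampled at 4 h: it rejects about 9% at 50 per arm and 13% at 100, nearly always in favour of Group B.
- Deaths counted to one common time in both arms: with no effect on anything the arms are exchangeable, and this fault goes.
- Deaths 30% v 15% with no marker effect: it rejects about 15% at 50 per arm and 27% at 100, because of the deaths alone.
- Deaths 20% in each arm, marker effect 0.40 SD, 50 per arm: power about 27%, against about 47% for a test of the second sample alone in survivors.

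**The case against.** The case against is that this is missing detail on secondary markers. The primary outcome is untouched, no early death rate is given, and the protocol does not say that the arms are sampled at different times. Dropping incomplete cases is a property of the usual procedure, not a statement in the plan.

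Much of that stands, and it rules out three stronger readings.

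- **A reader might infer that the survival requirement does differ by arm.** Item 5 permits this but does not say it. If blood is drawn at hour 6 in both arms, as the echocardiography is, the requirement is equal. The criterion on death before insertion would then remove nobody who could have had a second value.
- **A reader might infer that the comparisons are biased whenever early deaths differ.** Step 3 shows this fails in both directions. The bias needs early death to be related to the marker outcome.
- **A reader might simulate the second sample alone** and infer that a true benefit of 0.40 SD shrinks to 0.32 or 0.28 SD, with power of 33% for survivors only against 53% with worst ranks (20% v 10% deaths). Those figures ignore the baseline sample in Procedures item 3, which the GLM uses. With equal severity loading at both times the shrinkage disappears. The power comparison also credits worst ranks with detecting deaths.

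The objection does not remove the rest. Followed as written, the plan conditions on survival and permits unequal sampling times. Replacing the GLM with a mixed model would not by itself settle this, because it does not define a marker value after death.

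**Conclusion.** The concern holds in a limited form. The biomarker and lactate-clearance comparisons are conditional on survival to the second sample, and the protocol leaves open whether that sample falls at the same time since ROSC in both arms. If it does not, time since ROSC and the survival requirement both differ by arm. If it does, bias is still possible when early death is related to the marker change.

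The size cannot be derived from the documents. Over the assumed inputs (early deaths up to 30% v 10%, ρ from 0 to 0.6), the bias in change runs from none to roughly 0.1 to 0.2 SD. The upper end needs both a large difference in early deaths and a strong link between death and change. In-hospital mortality is unaffected. The plan should be amended on this point, but the primary comparison does not depend on it.

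**What to change.** 1. Reconcile Procedures item 5 so that the second blood sample used for the between-arm comparison is at one stated time since ROSC in both arms. The repeat echocardiography already uses hour 6. A post-insertion sample, if wanted, can be kept as a description of Group B.
2. Keep the planned analysis, name the contrast of interest, and describe the result as conditional on survival to the second sample. Report by arm the number without a second sample and the reason.
3. Add one supportive Mann-Whitney analysis over all randomised patients, in which anyone dead by that same common time, in either arm, gets the worst rank. State beforehand which direction is worse for each marker.

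The cost is a few lines of text and one table. The supportive analysis has two drawbacks. It tests death and marker together, so it can reject because of deaths alone (about 15% at 50 per arm with 30% v 15% deaths and no marker effect). It also has less power when early deaths are equal (about 27% against 47% for the second-sample-only test at 20% each). It must not be read on its own as evidence of a biomarker effect.

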### **Primary Outcome**

In-hospital mortality

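### In-hospital death, the primary outcome, is assigned a mean ± SD and a t test, against the plan's own rule for categorical data, and that rule's alternative test is undefined

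*Combined protocol and SAP*

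**What the plan says.** The Primary Outcome section consists of one entry, "In-hospital mortality". The Procedures section describes two randomised groups and states that "Research subjects will be monitored during hospitalization".

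The Analysis Method section opens with a general principle: "Data taken during the study will be displayed according to the variable type". It then gives three rules.

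- **Normal numerical data.** "Numerical variables with normal distribution will be displayed as mean" ± standard deviation. Variables measured repeatedly go to a general linear model. The rest go to "independent t test for data with one time measurement (mortality rate in hospital and effective lactate clearance". Mortality is named here.
- **Non-normal numerical data.** "Numerical variables with abnormal distribution will be shown in median (minimum-maximum) and then analyzed by Mann-Whitney test".
- **Categorical data.** "The categorical variable will be displayed as a percentage (number) and will be analyzed by chi-square test or alternate test".

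The alternative to chi-square is not named, and no condition for using it is given. The section does not commit to an effect estimate or a confidence interval for mortality.

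**The concern.** In-hospital death is recorded once per patient, as died or survived. A mortality rate is one number per group. A t test needs patient-level values with a within-group SD, and for mortality those values can only be 0 or 1. By the plan's principle that the variable's type decides its handling, mortality belongs under the categorical rule, yet it is listed by name under the normal numerical rule. The primary outcome therefore has two incompatible instructions.

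Neither route gives a complete primary analysis:

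- **Numerical route.** 0/1 values cannot be normally distributed. Read literally, the plan then sends mortality to the median and Mann-Whitney rule, which can hide the death rates altogether.
- **Categorical route.** The test that may replace chi-square, and the trigger for replacing it, are left open. The choice could be made after the deaths are counted, and it can decide whether a borderline result falls below 0.05.

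**Working it through.** **Inputs.** From the documents: two groups, a died/survived outcome, and the three display-and-test rules above. The plan gives no sample size, allocation ratio, significance level, death rates or effect size, so there is no stated figure to reproduce. Assumed for illustration: equal arms of 20, 30 or 50; death rates between 30% and 60%; two-sided 0.05.

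**1. How each rule displays the result.**

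| Deaths | Number (%) | Mean ± SD | Median (min-max) |
|---|---|---|---|
| 18/30 v 10/30 | 60% v 33% | 0.60 ± 0.50 v 0.33 ± 0.48 | 1 (0-1) v 0 (0-1) |
| 14/30 v 4/30 | 47% v 13% | 0.47 ± 0.51 v 0.13 ± 0.35 | 0 (0-1) v 0 (0-1) |

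The SD of a 0/1 variable is √[n·p(1−p)/(n−1)]. For 18/30 it is √(30 × 0.24/29) = 0.50, so it adds nothing to the proportion. In the second row Pearson p = 0.005, yet the medians are identical.

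**2. What each test gives for 18/30 v 10/30.**

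- t test: pooled variance (30 × 0.24 + 30 × 0.2222)/58 = 0.2391; SE = √(0.2391 × 2/30) = 0.1262; t = 0.2667/0.1262 = 2.11 on 58 df; p = 0.039.
- Pearson: X² = 60 × (18×20 − 12×10)²/(30×30×28×32) = 60 × 240²/806,400 = 4.29; p = 0.038.
- Yates: 60 × (240 − 30)²/806,400 = 3.28; p = 0.070.
- Fisher exact: p = 0.069.
- Mann-Whitney (normal approximation, continuity-corrected): p = 0.041.

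The risk difference is 0.267, with 95% CI 0.014 to 0.519 (t-based) or 0.015 to 0.476 (Newcombe). The same pattern holds for 30/50 v 20/50: t 0.046, Pearson 0.046, Fisher 0.071, Yates 0.072.

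**3. Why t and Pearson agree.** On 0/1 data with pooled variance, t² = X²(N−2)/(N−X²). Here 4.2857 × 58/55.714 = 4.46 = 2.11². For N = 60 the t test's 0.05 cut-off (t = 2.0017) corresponds to X² = 60 × 4.007/(58 + 4.007) = 3.88, against Pearson's 3.84. Few tables can fall in that gap.

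**4. How often the choice of test matters.** All 2×2 tables were enumerated and weighted by binomial probabilities. The death-rate pairs were 50/50, 60/60 and 30/30 (no effect), and 60/35, 60/40 and 50/30 (effect).

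| Comparison at 0.05 | Share of trials in which the tests disagree |
|---|---|
| t v Pearson | none at 20 or 30 per arm; under 0.002% at 50 (only 11/50 v 4/50 and its mirror images) |
| Mann-Whitney (continuity-corrected) v Pearson | 0.3% to 2.3% at 20 per arm; 0.0% to one decimal at 30 and 50 |
| Pearson v Fisher, no effect | 1.9% to 2.9% |
| Pearson v Fisher, effect | 7.1% to 10.5% |

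For 60% v 35%, Pearson and Fisher disagree in 10.1%, 10.5% and 7.1% of trials at 20, 30 and 50 per arm. Type I error is 0.043 to 0.057 for t and Pearson and 0.020 to 0.035 for Fisher.

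**5. How much disagreement an expected-count rule would leave.** Pearson v Fisher disagreements in tables with an expected count below 5 make up at most 0.3% of trials at 20 per arm (30% v 30%), and about 0.01% or less at 30 and 50. Nearly all the disagreement in step 4 lies in tables where such a rule would simply apply Pearson.

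**The case against.** The strongest reply is that the misassignment has almost no effect on inference. Steps 3 and 4 bear this out: t and Pearson give practically the same decisions and the same type I error. A 0/1 mean of 0.60 is also the 60% death rate, so under the rule that names mortality the format is poor but no information is lost. These points stand.

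It can also be said that the 7.1% to 10.5% figure belongs to the undefined alternative and not to the t test, and that it falls to 0.3% or less if the alternative means Fisher for small expected counts. That is also correct, but the plan states no such condition, so the freedom remains.

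The median display and Mann-Whitney arise only if the normality condition is applied literally to mortality, which the plan does not say will happen. The Mann-Whitney disagreement at 20 per arm also depends on a continuity correction that the plan does not specify; without it, the disagreement with Pearson at that size is zero. This route is a possible reading, not the expected one.

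Equal arms are assumed throughout. The identity in step 3 holds for any allocation with a pooled-variance t test. The enumeration, and an unequal-variance t test with unequal arms, were not examined beyond equal allocation.

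Finally, the listing may be a drafting slip, given the principle that variable type decides. However, mortality is named explicitly, and correcting the slip would still leave the alternative test undefined.

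**Conclusion.** The concern holds. As written, the primary outcome is handled as a normal numerical variable, in conflict with the plan's own categorical rule, and nothing elsewhere resolves it. This is an error in the text and not just missing detail.

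The damage from the t test is negligible under the conditions examined. The larger exposure is the undefined alternative. If the test were chosen freely after seeing the data, Pearson and Fisher would lead to different conclusions in 1.9% to 2.9% of trials with no effect and 7.1% to 10.5% with an effect. These are worst-case figures for that wording and rest on assumed equal arms of 20 to 50 and death rates of 30% to 60%. The missing effect estimate with a confidence interval is a separate, smaller gap in the same section. The point should be corrected, but it does not undermine the trial.

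**What to change.** In the Analysis Method section, remove mortality from the t-test list and state one primary analysis, for example:

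> In-hospital death (yes/no) will be shown as number (%) by randomised group and compared by Pearson chi-square without continuity correction. Fisher's exact test replaces it only if any expected count is below 5. The risk difference will be reported with a 95% confidence interval.

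For 18/30 v 10/30 the smallest expected count is 30 × 28/60 = 14, so Pearson applies and no choice remains. Other rules would serve equally well, provided one is fixed in advance. An adjusted analysis is optional and not part of this correction.

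The cost is a few sentences, with no new data, visits or patients. The wording should be settled before outcome data are examined.

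### Lactate is measured twice but analysed only as an undefined clearance with no baseline adjustment, which costs some efficiency on a non-primary marker

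*Combined protocol and SAP*

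**What the plan says.** Procedures, item 3, includes lactate in the baseline bloods: "Laboratory tests for peripheral venous blood include: Lactate levels, urea (Ur), creatinine (Cr". Item 5 repeats it: "Laboratory tests for peripheral venous blood include lactate, IL-6, beclin-1 and caspase 3 levels". The timing of that second draw is given as "Blood sampling is repeated at 6th hour post ROSC or 1 hour post-insertion of IABP".

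The Analysis Method section assigns a "general linear model (GLM) test for data measured more than once" and names five variables: IL-6, beclin-1, caspase-3, a-vO2 difference and ScvO2. Lactate is not among them, although IL-6, beclin-1 and caspase-3 come from the same two peripheral venous draws. Lactate appears only as a clearance, under "independent t test for data with one time measurement (mortality rate in hospital and effective lactate clearance". Two fallback rules follow. For skewed numerical data: "Numerical variables with abnormal distribution will be shown in median (minimum-maximum) and then analyzed by Mann-Whitney test". For categorical variables, the plan says they "will be analyzed by chi-square test or alternate test".

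Neither section gives a formula, time window or cut-off for clearance, or an adjustment for baseline lactate. The only stated primary outcome is "In-hospital mortality".

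**The concern.** A before-and-after pair is reduced to one derived number per patient, and the arms are compared on that number alone. If clearance is the percentage fall from the first value, the scale is lopsided: the best possible score is +100%, and there is no lower limit. Patients with a low first lactate can produce very large negative scores, and part of the spread between patients simply reflects where they started.

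The Aim section looks for benefit through better circulation and tissue perfusion. It does not name lactate, but lactate is one of the few planned measurements that bear on perfusion. An inefficient comparison makes a real effect on it easier to miss, and an undefined variable leaves the formula open until the data have been seen.

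**Working it through.** **Inputs.** From the documents: two lactate values per patient, clearance compared by t test or Mann-Whitney, and no baseline adjustment. Not in the documents: sample size, alpha, effect, SD, correlation and the clearance formula. There is therefore no planned figure to reproduce, and everything numerical below is illustration. Clearance is assumed to be 100 × (first − second) / first.

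**Step 1: is the first lactate used?** Yes. With a second value of 3.0, a first value of 4 gives (4 − 3)/4 = 25%, and a first value of 10 gives (10 − 3)/10 = 70%.

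**Step 2: shape of the scale.** A rise from 1.2 to 2.4 scores (1.2 − 2.4)/1.2 = −100%. A fall from 12 to 6 scores +50%. One doubling and two halvings average (−100 + 50 + 50)/3 = 0, as if nothing had happened. As ratios, the same three patients give (2 × 0.5 × 0.5)^(1/3) = 0.79, a fall of about 21%.

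**Step 3: does dividing by baseline remove its influence?** No. In simulated lognormal lactate (log-SD 0.6 at both times, average fall about 30%), clearance still correlates with log first lactate: 0.52, 0.46, 0.37 and 0.22 when the first-to-second correlation r is 0.3, 0.5, 0.7 and 0.9.

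**Step 4: closed form on the log scale.** With equal SDs at the two times, and relative to analysing the second value alone, the variance factor is 2(1 − r) for the log ratio and 1 − r² for baseline adjustment. For an effect of 0.5 SD, two-sided 5% and 80% power, patients per arm are:

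| r | log ratio | baseline-adjusted |
|---|---|---|
| 0.3 | 88 | 58 |
| 0.5 | 63 | 48 |
| 0.7 | 38 | 33 |
| 0.9 | 13 | 12 |

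The ratio of the two factors is 2/(1 + r), so adjustment is never worse in this setting and the advantage fades as r approaches 1.

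**Step 5: simulation of the plan as written, including its fallback.** Assumptions: lognormal lactate with median 6 at the first sample, log-SD 0.6 then 0.7, second lactate 30% lower on treatment than on control, 50 per arm, two-sided 5%. The plan does not say how normality is judged; a Shapiro test was assumed. It flagged 97–100% of simulated trials, so Mann-Whitney would nearly always be used on such data.

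| r | t test on clearance | plan with fallback | log second lactate, adjusted for log first | gain over plan |
|---|---|---|---|---|
| 0.4 | 59% | 67% | 79% | 12 points |
| 0.6 | 80% | 84% | 89% | 5 points |
| 0.8 | 97% | 98% | 98% | none |

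With 30 per arm, the plan with its fallback reaches 46%, 61% and 89%, against 55%, 68% and 89% adjusted. A further run of the same simulation, made for this write-up, agreed within simulation error. With no treatment effect, rejection rates were about 5% for every method.

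**The case against.** **The first lactate is not thrown away.** A reader might infer from the one-time label that it is. The documents do not support that: clearance in its ordinary sense is computed from both values, and one derived number per patient is a reasonable thing to list as a single measurement. This stands. The criticism is of how the first value is used.

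**The plan has a fallback for skewed data.** Mann-Whitney answers much of the complaint about extreme negative scores, and quoting t-test power alone would overstate the loss (59% against 79% at r = 0.4, where the plan as written reaches 67%). This stands too, which is why the comparison rests on the fallback. It narrows the gap without closing it, because ranking clearance does not adjust for baseline.

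**Effective might mean a yes/no threshold.** A reader could then say that the t test is the wrong test and that dichotomising wastes information. The documents give no cut-off, and clearance sits in the sentence on numerical variables, so a number is the more natural reading. If a category was meant, the plan's own rule is chi-square or an alternative, and the t-test assignment would conflict with it. No loss is claimed here on that reading.

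**Clearance is the investigators' choice of metric, and lactate is not primary.** Both true. This limits the severity but does not remove the efficiency argument.

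**Other problems are larger.** The same sentence puts in-hospital mortality, a binary primary outcome, under a t test, which is more serious and separate. The two alternative times for the second sample may give the arms different clearance windows, and a death before that sample leaves lactate missing. Baseline adjustment cures neither.

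**Conclusion.** The point holds as a modest improvement in efficiency and clarity. Lactate is available at two times, yet the plan compares only an undefined clearance, unadjusted for baseline. Under the stated assumptions with 50 per arm, adjusting log second lactate for log first lactate gains about 12 points of power at a correlation of 0.4, 5 at 0.6 and none at 0.8. These figures depend on an assumed SD, effect, sample size, correlation and normality check, none of which the documents supply, so the actual gain in this trial cannot be stated.

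It would be wrong to infer that the planned test is invalid or inflates false positives: type I error is about 5% whichever method is used. Severity is low to moderate, because lactate is not the primary outcome.

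**What to change.** In the Analysis Method section:

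1. Take effective lactate clearance out of the list of one-time measurements compared by t test.
2. Analyse log lactate at the second sample with a linear model containing arm and log baseline lactate. This belongs to the general linear model family that the plan already names.
3. Report the between-arm ratio of geometric means with its 95% CI.
4. Keep percent clearance as a descriptive summary, with its formula and the two sampling times stated. If a threshold version was intended, say so, give the cut-off, and place it under the rule for categorical variables.

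The sampling times in Procedures, item 5, should be reconciled and the handling of deaths before the second sample stated; those are separate edits.

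The cost is wording only, since both lactate values are already collected. The one drawback is that the main lactate result becomes a ratio instead of the more familiar clearance percentage.
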